Title of the Proposal:

"Project 500" CHILD Study

STUDY METRICS:

Planned number of subjects:	In total, the CHILD Study recruited 3,629 families and 3,350 children are currently being followed. We plan to test several key hypotheses by analyzing 1 year outcomes in a subset of 500 children in whom we now have complete datasets to that age.
How long will it take to write and submit protocol to IRB/IEC (in months)?	REB approvals for the full CHILD Study have been received at all four recruitment sites – Vancouver, Edmonton, Winnipeg, Toronto – and at the National Coordinating Centre in Hamilton. All are current. No additional ethical approval is required to undertake the analyses proposed.
Projected Start Date (after IRB/IEC and contracting are complete):	Project 500 will commence as soon as funding is obtained to perform the biological analyses.
Expected accrual rate (# of subject/month):	Recruitment of the full CHILD cohort was completed in 2012.
Projected enrollment timelines: Please specify - Date first subject enrolled (mm/yyyy): - Date Last subject enrolled (mm/yyyy): - Follow-up time (in months):	The cohort is fully enrolled. The 500 children selected for this project have all the required data and samples now available. Follow-up of all CHILD subjects is planned until infants are aged 5 years but this specific project is examining outcomes in the first year of life.
Target time of the first formal analysis (mm/yyyy):	June 2015
Target time of the final report (mm/yyyy):	June 2016
Time to generate draft manuscript or poster/abstract (in months):	3 months
Target Publication or Conference (include mm/yyyy):	Data will be presented at national (AllerGen, CSACI) and international (ATS, ERS) conferences 2015-16.

Purpose and rationale for the study:

This proposal relates to the testing of several specific hypotheses in a subset of 500 participants in the Canadian Healthy Infant Longitudinal Development (CHILD) Study. These 500 now have complete data from the time of recruitment (in pregnancy) to age 1 year. The primary purpose of this proposal is to identify risk factors for early allergic outcomes and biomarkers that may predict future disease. These 500 infants will provide critical preliminary data, not only related to early outcomes, but also to inform analytical plans for the full CHILD cohort.

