The objective of Project 500 is to carefully analyze a complete set of multiple clinical and environmental questionnaires and selected infant biological samples pertinent to early clinical outcomes (up to age 1 year). The **primary clinical outcomes are recurrent episodes of wheezing and development of atopy by age 1 year**. Atopy is defined by skin allergen responses. Secondary outcomes include atopic dermatitis or eczema, and reported food allergy. We propose detailed exploration of patterns of clinical illnesses and will correlate these with analysis of multiple biomarkers to determine their predictive power.

There is good evidence from longitudinal epidemiological studies and from clinical trials that allergy is both a common precursor to childhood asthma and also a predictor of persistence of childhood asthma into adulthood. The “atopic march” is a well recognized phenomenon in which children develop atopic dermatitis and/or food allergy in early childhood, and then go on to have recurrent wheezing and persistent atopic asthma in later childhood and adulthood. Our selection of specific hypotheses for examination in Project 500 reflects this phenomenon.

Four specific hypotheses will be tested in “Project 500”:

1. **Maternal diet in pregnancy influences food sensitization in infancy; specifically avoidance of foods (e.g. peanuts) is associated with intolerance to that food.**

Research on diet and interventions to prevent atopic disease have focused on foods with anti-inflammatory properties (e.g. n-3 fatty acids), antioxidants (vitamin E and zinc), and vitamin D. Recent

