3. Sensitization to cow's milk, egg or peanut, together or separately, at 1 year is a major risk factor for wheezing episodes in early infancy.

Sensitization to foods has been associated with an increased risk for asthma (Rhodes et al, J Allergy Clin Immunol. 2001;108:720-5 and has recently been included in a modified Asthma Predictive Index (mAPI) (NEJM 2006;354:1985-97). The mAPI and an m2API have been validated in a small cohort as good predictors for persistent asthma at school age (Chang T et al, J Allergy Clin Immunol: In Practice 2013; 1:152-156). As yet unpublished data from a Canadian cohort show a substantial increased risk (OR 8-10) of persistent asthma in children with sensitization to a food in the first year of life (verbal communication, [name]). We will be able, using CHILD Study data, to examine these early life sensitization patterns in relation to the occurrence of wheezing episodes, and not only determine immediate relationships but also follow the children for several years to validate (or not) the Asthma Predictive Index.

4. Exposures to oxidizing agents in the prenatal period and during the first 3 months of life influence the development of atopy and wheeze at 1 year.

Infants raised in Canada spend a large majority of time indoors at home. Multiple indoor air exposures have been associated with wheeze and asthma, environmental tobacco smoke (ETS) being the most widely recognized. Oxides of nitrogen, associated with gas cooking and heating, are linked with worsening asthma. Innate immune inflammatory response can be activated by common indoor exposures, including trichloramines, aldehydes (e.g., formaldehyde) and other volatile organic compounds (VOCs) in home furnishings and cleaning products.

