--------------	---

	
[3] Sensitization to cow's milk, egg or peanut, together or separately, at 1 year is a major risk factor for wheezing episodes in early infancy.
 
Epicutaneous testing at 1 year of age is performed to common food allergens including cow's milk, egg and peanut. A positive test (≥ 2 mm wheal response greater than the negative control) will define sensitization regardless of the presence of a positive history of an allergic reaction (i.e. history negative skin test positive). A definition of food allergy requires the presence of a positive test for allergen specific IgE and a positive history of a clinical allergic reaction or, in the absence of known exposure to that food, a positive skin test and an ex vivo measurement of allergen-specific IgE at a level defined to represent the 95th percentile or higher for a positive challenge to that food.
 
[4] Exposures to oxidizing agents in the prenatal period and during the first 3 months of life influence the development of atopy and wheeze at 1 year.
 
Data sources: A comprehensive baseline questionnaire (during pregnancy) and updates at 3 months, 1, 3, and 5 years of age record residential address, housing structure, function, condition, maintenance and cleaning habits, presence and use of attached garage, renovations, source and extent of dampness, mold growth, new furnishings, appliance and household cleaner emissions, presence and type of air conditioning and cleaning, and conditions of use. Questions related to the child's and families' time activity include time spent in different rooms in the house and indoors vs. outdoors, time in transit, mode of transport, frequency/duration of visits to daycare, indoor pools and exposure to smoke. Shorter questionnaires at 6 and 18 months, 2, 2.5, and 4 years of age focused on child time-activity and major changes including renovations. When the infant was 3-4 months old, research staff trained by Canada Mortgage and Housing Corporation and the CHILD Environmental Working Group visited the home. This enabled measurement of geographical coordinates (GPS) for assigning air pollution and traffic-related air pollution (TRAP) exposure, evaluation of the structure, function and exposure sources within the home with emphasis on cleanliness and cleanability, furnishings, ventilation (air conditioning, heating, cooling), potential for moisture build-up, microbial and chemical contaminant burdens, basement conditions and potential for air exchange with the outside and with attached garages. The breadth of exposures characterized will enable development of novel exposure indices for integrating multiple oxidative and/or inflammatory exposures to better capture total risk posed by the physical environment.
 
Indoor Exposures: Questionnaires included animal exposures (dogs, cats, other pets) at multiple time points. Dampness (water leaks) and mold were also assessed by repeated questionnaires, and visual inspection of the home. Home (most used room) and child's bedroom dust was systematically sampled with a specially designed vacuum system, weighed, sieved and stored at -80C. A subset of the fine dust has been analyzed for endotoxin and β-glucans to support questionnaire validation and application in regards to dampness and mold. A range of organic chemicals are also being quantified (e.g., phthalates, PAHs) at Environment Canada laboratories. We propose to analyze dust for dog, cat, and house dust mite allergens; all children are skin-tested for these and other inhalant allergens at 1, 3 and 5 years of age. Urine collected at 3

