Statistical justification for the study design, sample size calculation, and statistical analysis plan	
For Project 500, we have selected 500 children in whom we now have complete data to age 1 year. These will comprise approximately 125 children from each of the recruitment sites to minimize geographic bias. At age 1 year, the dominant clinical outcomes of relevance are wheezing (as defined as a positive response to ever wheeze on 3, 6 or 12 month questionnaires), atopic dermatitis and reported food allergy, and objective evidence of sensitization to food and inhalant allergens assessed by skin testing (≥ 2mm wheal response to epicutaneous testing). We currently have little information on biological data at 1 year, as it is rare for normal children to have blood taken at this age. It is even less common to have a population of healthy normal children providing blood, urine, stool, nasal secretions, and skin allergy tests, to examine correlates of biomarkers with these outcomes. Hence power calculations for this sample of 500 are difficult, but the planned analyses will provide preliminary data which will allow calculations of appropriate sample sizes for future analyses in the full cohort. We anticipate approximately 50 of these 500 children will have experienced wheezing in the first year of life, and a similar number will have developed atopic dermatitis.
 
For the full CHILD Study, the primary outcome is physician-confirmed asthma at age 5 years, with multiple pre-specified intermediate and secondary outcomes. Recruitment and follow-up of over 3,000 families from the general population will allow well-powered integrated analyses involving derivation of new multi-exposure indices; examining the effect of respiratory infections on growth of infant pulmonary function; identification of innate and adaptive immune phenotypes in relation to environmental exposures; linkage of epigenetic profiles to maternal stress, socioeconomic status, environmental exposures and viral infections; and determining impact of nutritional factors including maternal diet, breast-feeding, infant diet, transition to table foods and the role of probiotics and nutraceuticals on immune function through the infant microbiome. The comprehensive longitudinal assessments within CHILD allow sophisticated statistical modeling, including longitudinal latent class analysis, structural equation modeling and factor analysis to assess specific pathways relating genetics, SES, immunity, environment and nutrition to the development of allergy and asthma.
 
The statistical analyses for Project 500 will include a number of statistical approaches, including logistic regression (Agresti, 2012), generalized linear models, and generalized linear mixed models (McCulloch et al., 2008). Both

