
	
univariate and multivariate analyses will be employed, and the effects of potential confounders will be investigated through multivariable analyses.
 
All exposure and outcome variables will be first examined, prior to statistical modeling. For continuous measures (e.g. vitamin D intake during pregnancy in Hypothesis 1, serum 25-hydroxyvitamin D in infancy in Hypothesis 2, indoor concentrations of endotoxin and β-glucans in Hypothesis 4), the distributions (including mean, median, range, variance, etc) will be described and then used for determining the appropriateness of possible modifications to measures (e.g., log transformation for non-normality, or categorizing values using cut-offs based on both statistical and clinical/biological reasons); for categorical measures (e.g., development of wheezing at 1 year in Hypothesis 2, positive results for peanut sensitization in skin tests in Hypothesis 3, and development of atopy at 1 year in Hypothesis 4), frequencies and percentiles will be summarized and used to determine choices of statistical methods (e.g., exact methods for sparse data, if applicable).
 
Specifically, for Hypothesis 1, the association between intolerance to certain foods (e.g. peanut) and maternal diet (e.g. exposure to nuts) will be examined first using bivariable logistic regression analysis; here the outcome (binary) variable is intolerance (e.g. to peanuts, yes/no), and the explanatory variable is diet (e.g. avoidance of peanuts, n-3 fatty acid intake), which can be either a binary (yes/no), a categorical (low/medium/high) or a continuous variable. When considering the effects of covariates, such as gender and maternal atopy, on the association being investigated, multivariable logistic regression analysis will be employed, and potential confounders such as ethnicity will be accounted for in the regression model.
 
Similar approaches will be employed in the analyses of the other hypotheses. For Hypothesis 2, the outcome variable, development of early childhood wheezing (yes/no), will be determined at 1 year, and the measure of serum 25-hydroxyvitamin D status [25(OH)D] will be examined for its distribution and, if necessary, categorized as an ordinal variable (e.g. low/medium/high based on statistical and clinical/biological thresholds). Results based on ordinal categorization will likely provide an intuitive interpretation of the association (e.g. quantifying an n-fold increase in risk for developing childhood wheezing when comparing high vs. low 25(OH)D). As a primary exposure variable of interest, the distributions of 25(OH)D values will be compared between two groups, infants with vs. without wheezing, using nonparametric methods (e.g. Wilcoxon rank-sum test) and the t-test (if normally distributed); if the distribution exhibits a categorical trend, the chi-square test will be applied to evaluate the relationship with the outcome (childhood wheezing).
 
For Hypothesis 3, the association between the outcome variable, wheezing episodes in early infancy (any wheeze to 1 year), and sensitization to foods (positive test result) will be examined using regression models for categorical data. As described in the previous section “Study Design”, sensitization will be defined as a binary variable (positive/negative), and test results for single and multiple foods (e.g. sensitivity to egg and peanut) will be considered in the analyses, which will employ multiple indicators (so-called “dummy variables” for each of the foods tested). To investigate whether there are additive effects that combinations of sensitizations to different foods have on the frequency of

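### Hypothesis 3 calls food sensitization at 1 year a major risk factor for infant wheeze, but no wheeze is counted after sensitization is measured, so the analysis supports only a cross-sectional association

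*Protocol*

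**What the plan says.** The hypothesis appears twice in the same words, in the purpose and rationale section and again under Study Design: "Sensitization to cow's milk, egg or peanut, together or separately, at 1 year is a major risk factor for wheezing episodes in early infancy".

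- **Exposure.** Study Design, item 3: "Epicutaneous testing at 1 year of age is performed to common food allergens including" cow's milk, egg and peanut. A positive test defines sensitization. No earlier food skin test is described.
- **Outcome.** The statistical section relates "wheezing episodes in early infancy (any wheeze to 1 year), and sensitization to foods (positive test result") by regression models for categorical data. The same section defines "wheezing (as defined as a positive response to ever wheeze on 3, 6 or 12 month questionnaires").
- **Horizon.** Study Metrics says that "this specific project is examining outcomes in the first year of life". Follow-up to age 5 belongs to the full cohort.
- **Motivation.** The rationale says the hypotheses were chosen to reflect the atopic march, in which "children develop atopic dermatitis and/or food allergy in early childhood, and then go on to have recurrent wheezing" and later persistent asthma.

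**The concern.** A risk factor is ordinarily understood to come before the outcome, and the atopic march that motivates the hypothesis has that order: sensitization or food allergy first, wheeze afterwards. In Hypothesis 3 the exposure is measured at the end of the window over which the outcome is counted. Its timing is shared with Hypothesis 2, where serum is also drawn at 1 year, but Hypothesis 2 claims only an association. Hypothesis 3 alone joins an exposure measured at the end of the window to a claim that it is a major risk factor.

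What is at stake is the conclusion. A positive result could mean that sensitization leads to wheeze, that both share a cause such as family atopy, or that children who wheeze early go on to sensitize. A null result would say little about wheeze after sensitization is established, because wheeze after the test is not counted. The protocol intends Project 500 to inform analyses in the full cohort, so a first-year association reported as a risk factor would carry forward.

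**Working it through.** No sample size, power or alpha figure bears on this point, and the protocol gives no figure to reproduce. The check is a comparison of timings.

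**Inputs**

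| Item | Value | Source in the protocol |
|---|---|---|
| Food sensitization measured | 12 months | Study Design, item 3 |
| Wheeze ascertained | 3, 6 and 12 months | Statistical section, outcome definition |
| Hypothesis 3 outcome window | Birth to 12 months | Statistical section, Hypothesis 3 |
| Wheeze cases anticipated | About 50 of 500 | Statistical section |

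**Step 1. Outcome observation after the exposure is measured.** Last outcome time minus exposure time: 12 - 12 = 0 months.

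**Step 2. Lead of each wheeze report over the skin test.**
- 3-month questionnaire: 12 - 3 = 9 months before the test.
- 6-month questionnaire: 12 - 6 = 6 months before the test.
- 12-month questionnaire: 12 - 12 = 0 months, at the same nominal age as the test.

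**Step 3. Cases affected.** 50 / 500 = 10%. All of these are reported before or at the age at which sensitization is first measured, so the number that can be shown to follow it is 0 of about 50.

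**Step 4. Does any other part of the plan supply the order?** The Hypothesis 3 rationale mentions following the children for several years, but for validation of the Asthma Predictive Index. The analysis described for Hypothesis 3 stops at 1 year. Child diet is recorded at 3 and 6 months and 1 year, which can show when a food was introduced but not when sensitization to it began.

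**Step 5. Could later data be available in time?** If all 500 had reached 1 year by the document date of 15 April 2013, they were born by about April 2012 and turn 3 by about April 2015. The first analysis is set for June 2015, about 2 months later. The final report is set for June 2016, about 14 months later. Three-year data from the youngest children would be tight for the first analysis and more plausible for the final report.

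**The case against.** The strongest reply has four parts.

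1. **Measurement is not onset.** A positive test at 12 months marks a state acquired at some earlier, unknown time, and wheeze in the second half of the year may well have followed it. This stands. A reader might infer that the order is reversed, or that there is no follow-up after sensitization itself. The documents support neither. They show only that none follows its measurement and that the sequence is unknown.

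2. **The analysis section already speaks of an association.** This stands too. That association can be estimated, so it would be wrong to say that the analysis yields nothing. The defect is in the hypothesis statement, which claims more than its own analysis can deliver.

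3. **Alternative explanations are partly handled.** Maternal atopy is named as a covariate for Hypothesis 1, similar approaches are promised for the others, and infant diet is recorded. Adjustment can reduce measured confounding. It cannot supply temporal order.

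4. **The first-year horizon is a declared scope.** The project is presented as preliminary, and later asthma outcomes are placed in the full cohort. This stands, and it disposes of the most tempting stronger reading: that the cut-off is simply avoidable and that wheeze from 1 to 3 years should become the primary outcome. Several features of the document tell against that:
   - The funding section reports renewal for 2012-2014 and says that grants for continued follow-up are still to be sought.
   - The youngest children reach age 3 only about 2 months before the first analysis.
   - The questionnaires at 18 months, 2 and 2.5 years are described as focused on time-activity and major changes such as renovations. Project 500's text sets out no wheeze measure for that interval.
   - The atopic march as described extends into later childhood and adulthood, which a window from 1 to 3 years would not reach either.

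**Conclusion.** The wording of Hypothesis 3 is wrong for the design. With 0 months of outcome observation after the exposure is measured, and with about 50 anticipated cases all reported at or before that age, Project 500 can estimate a cross-sectional association between sensitization at 1 year and wheeze in the first year. It cannot show that sensitization preceded wheeze.

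This rests on two assumptions: that visits and questionnaires occur at their nominal ages, and that no food skin test exists before 1 year (none is described). A skin test done somewhat later than 12 months would not help, since no later wheeze report enters the outcome. The conclusion does not depend on effect size, power or alpha, and the count of 50 is the protocol's own expectation.

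The fault lies in the claim. The choice of a first-year outcome is legitimate for a preliminary project.

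**What to change.** 1. In the purpose and rationale section and in Study Design, item 3, replace the words that make sensitization a major risk factor with *is associated with*.
2. In the statistical section, label the Hypothesis 3 analysis as cross-sectional and state that it supports no inference about temporal order.
3. State that the risk-factor question will be tested on wheeze reported after the 1-year skin test, adjusted for wheeze before 1 year, in the continuing CHILD follow-up.
4. Optionally, add that analysis as secondary in the 500 if 3-year data are available by the final report. It should not replace the first-year outcome.

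**Cost.** Items 1 to 3 change text only and need no new visits, samples or data within Project 500. The price is a weaker conclusion on Hypothesis 3. Item 4 would need priority entry of 3-year questionnaires, confirmation that they capture wheeze since the 1-year visit, and acceptance of some loss to follow-up, whose size the protocol does not give.

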meta-analyses suggest beneficial effects for pre-natal vitamins A, D, and E, zinc, fruits and vegetables, and the Mediterranean diet. Nutrients may impact development of asthma through immune modulation or the child's intestinal microbiome. In spite of, or possibly because of, recommendations for early life avoidance of specific 'highly allergenic' foods including peanut in the 1990s from many national expert organizations (e.g. Canadian and British Pediatric Societies, American Academy of Pediatrics) there has been an explosion of food allergy, particularly to peanut in most high income countries (Miles and Buttriss, Nutrition Bulletin 2010). Intriguingly, studies have shown a very low prevalence of peanut allergy in Israel where peanut is commonly introduced in the first year of life compared with England where it is seldom introduced before the first birthday. This study accounted for a general heritable risk using children from a similar background (Ashkenazi Jewish) in both countries. (DuToit et al, JACI 2008). In the Danish National Birth Cohort maternal peanut (RR: 0.66; 95% CI: 0.44-0.98) and tree nut (RR: 0.83; 95% CI: 0.70-1.00) intake during pregnancy was associated with decreased risk of asthma in the child at 18 months of age. Intriguingly, there was no comment on the development of allergy in this cohort. The data we are collecting in the CHILD Study will allow us to examine the link between maternal intake of specific foods such as peanut and the outcome of allergy to that food in the infant.

2. Low serum 25-hydroxyvitamin D values in infancy are associated with development of early childhood wheezing.

Most, but not all, studies have demonstrated a relationship of maternal vitamin D insufficiency with wheezing in pre-school children. A meta-analysis of four large cohort studies found that high maternal vitamin D intake during pregnancy was protective against wheeze in children. However, a recent publication from the ALSPAC cohort shows an association of increased wheeze with increased vitamin D levels. One issue may well be polymorphisms of the Vitamin D receptor in the mother (associated with vitamin D levels during pregnancy) and in their offspring during the few years of life. The data obtained in the CHILD Study will provide the opportunity to confirm or negate the associations between levels of vitamin D and wheezing syndromes in early childhood.

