Study Design	
CHILD Study Methods: Pregnant women from the general population were recruited in the second and third trimester of pregnancy in multiple urban and rural centres; they reflect ethnically, environmentally, socioeconomically and culturally diverse families with over 25% non-Caucasian parents. Children currently range from those recently born up to 5 years old.
 
Children are assessed at delivery, at a 3-month home visit, and at 1, 3, and 5 years of age. Repeated and diverse environmental and health questionnaires combined with objective measurements (allergy skin prick tests, lung function) detailed home inspection, and a rigorously annotated bank of biological samples from parents (venous blood, breast milk), index child (cord and venous blood, stool, urine, nasal secretions) and home (dust) provide a robust, comprehensive database for testing of multiple interrelated hypotheses.
 
Specific methods pertinent to the current analyses:
 
Data entry related to events prior to the 1 year assessment have been completed as a priority for these 500 children, and data entry for all 1 year questionnaires and samples given priority. Questionnaire data will then be accessed from HealthDiary, cleaned and assembled by an experienced Data Manager. 500 dust samples and 1500 blood samples (mother, cord blood, child at 1 year) will be identified and retrieved for analyses. Dust analyses will be undertaken at the laboratory of [name], University of Toronto, and blood analyses at the Clinical Trials and Clinical Research Laboratory, Hamilton. Teams of CHILD investigators will analyze the resulting data in collaboration with local statisticians and with our Senior Statistician, [name], Canada Research Chair in Statistical Methods for Health Care, University of Toronto.
 
[1] Maternal diet in pregnancy influences food sensitization in infancy, specifically avoidance of foods (e.g. peanuts) is associated with intolerance to that food.
 
Pre- and post-natal nutrition has been collected using maternal and infant/child questionnaires including exclusive and non-exclusive breast-feeding, age of first supplementation and age of introduction of solid foods. A Food Frequency Questionnaire (FFQ) developed by nutritional epidemiologists at the Fred Hutchinson Cancer Research Center, based on questionnaires used in US studies was modified to reflect Canadian ethnic food choices. Further, the database developed by the University of Minnesota Nutrition Data Systems for Research for data entry and nutrient analysis was “Canadianized” for use in CHILD. This self-administered FFQ asks pregnant mothers to report the frequency of consumption and portion size of approximately 175 line items during their pregnancy, and was completed by the mother at the time of enrollment. At age 3 and 6 months and 1 year, child diet was recorded, including exposure to cow’s milk, eggs and nuts.
 
[2] Low serum 25-hydroxyvitamin D values in infancy are associated with development of early childhood wheezing.
 
Serum is obtained from children at age 1 year; vitamin D will be measured by standard assay methods at the research laboratories at the Hospital for Sick Children. Recurrent wheezing will be identified from questionnaires completed by mother when the child is 3, 6 and 12 months of age.

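### Hypothesis 2 takes 25(OH)D from a sample at age 1 year and wheeze from reports up to that age, so it can estimate a cross-sectional association but not a risk of developing wheeze

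*Protocol*

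**What the plan says.** The hypothesis reads: "Low serum 25-hydroxyvitamin D values in infancy are associated with development of early childhood wheezing".

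- **Exposure.** Study Design, under Hypothesis 2: "Serum is obtained from children at age 1 year; vitamin D will be measured by standard assay methods". No other 25(OH)D measurement is named for this hypothesis.
- **Outcome.** The same paragraph: "Recurrent wheezing will be identified from questionnaires completed by mother when the child is 3, 6 and 12 months of age". The statistical section defines wheezing "as defined as a positive response to ever wheeze on 3, 6 or 12 month questionnaires", and for Hypothesis 2 says that "the outcome variable, development of early childhood wheezing (yes/no), will be determined at 1 year".
- **Window.** The Study Metrics table limits this project to outcomes in the first year, while the cohort is followed to age 5.
- **Interpretation.** The statistical section makes 25(OH)D a primary exposure. As an example of an intuitive result, it offers a fold-increase in the risk of coming to wheeze between 25(OH)D categories. The Primary Objective of Project 500 is to find predictors of early outcomes. The Hypothesis 2 rationale says the CHILD data "will provide the opportunity to confirm or negate the associations between levels of vitamin D and wheezing syndromes in early childhood".
- **Earlier blood.** Study Design also says that "500 dust samples and 1500 blood samples (mother, cord blood, child at 1 year) will be identified and retrieved for analyses". Neither the methods nor the analysis of Hypothesis 2 uses the maternal or cord samples.

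**The concern.** A statement about the risk of developing an outcome needs the exposure to be measured, or at least known to be fixed, before the outcome occurs. Here the exposure is measured last. If earlier wheezing changes time outdoors, feeding or supplement use, the 1-year level may partly be a result of wheeze. Such an effect could run either way: less time outdoors might lower the level and create an inverse association, while supplements started after illness might raise it and hide one.

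At stake is the conclusion drawn from one of the four named hypotheses. An inverse association written up as a raised risk of developing wheeze would claim more than the data show. A null would not rule out an earlier effect of low vitamin D. The Protocol intends Project 500 to inform the full-cohort analyses, so an over-read result would carry forward. Nothing in the Protocol acknowledges the time order.

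**Working it through.** **Time order.** The Protocol gives the ages, so the gap between each wheeze report and the sample follows directly:

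- 3-month questionnaire: 12 − 3 = 9 months before the sample.
- 6-month questionnaire: 12 − 6 = 6 months before the sample.
- 12-month questionnaire: 12 − 12 = 0, so about the same age, and the question looks back over wheeze already experienced.

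No counted wheeze is clearly later than the sample. The exact dates of the draw and the 12-month questionnaire are not given, so the last item is best described as concurrent. Study Design speaks of recurrent wheeze and the statistical section of ever wheeze, but the time order is the same under either definition.

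**Is there a figure in the plan to reproduce?** No. The statistical section says power calculations are difficult and states no alpha, power or effect size. Its only usable figure is the anticipated 50 wheezers among 500, that is 50/500 = 10%.

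**What the planned comparison can detect.** Assume two-sided alpha 0.05, 80% power, and 50 wheezers against 450 others.

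- Standard error of the mean difference in SD units: √(1/50 + 1/450) = √0.02222 = 0.149.
- Detectable shift: (1.96 + 0.842) × 0.149 = 0.418 SD.
- As an odds ratio per SD: exp(0.418) = 1.52.

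This is a detectable effect. It says nothing about how large any bias is.

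**Illustration of reverse causation.** Suppose vitamin D has no effect on wheeze, and earlier wheeze lowers 1-year 25(OH)D by d SD. The chance of a significant result is about Φ(d/0.149 − 1.96):

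- d = 0.2: Φ(1.34 − 1.96) = Φ(−0.62) ≈ 27%.
- d = 0.3: Φ(2.01 − 1.96) = Φ(0.05) ≈ 52%.
- d = 0.5: Φ(3.35 − 1.96) = Φ(1.39) ≈ 92%.

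Simulating the planned Wilcoxon test (2,000 studies per value of d) gave 26%, 49% and 91%, with median odds ratios for the lowest against the highest tertile of about 1.5, 1.9 and 2.9. With d = 0 the test rejected in 4.4% and the median odds ratio was 1.0. Because the test is two-sided, an upward shift of the same size would be significant equally often, with the association reversed. An upward shift that matched a true deficit would cancel it: −0.3 + 0.3 = 0. All values of d are assumptions; the Protocol gives none.

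**The case against.** The strongest defence is that Hypothesis 2 speaks of association, whereas Hypotheses 1 and 4 speak of influence. The rationale also refers to associations, and the fold-increase phrase is only an example of how an association might be read. A cross-sectional association can be estimated from these data. This stands: a reader might infer that Hypothesis 2 cannot be tested at all, and the documents do not support that. What remains is that the hypothesis also speaks of development, and the statistical section and the Primary Objective look forward in time.

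Second, no passage says that wheeze changes 25(OH)D. This also stands. A reader might take 0.42 SD or an odds ratio of 1.52 as the size of the bias, but these are detectable effects under assumed alpha and power.

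Third, the Protocol records time-activity and infant diet during year 1 and plans adjustment for confounders. These data help, but they are not named as covariates for Hypothesis 2, and adjustment does not put the exposure before the outcome.

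Fourth, a reader might infer that cord or maternal 25(OH)D must become the primary exposure. The hypothesis concerns values in infancy, so that would replace the question. Sample volume and assay cost cannot be checked from the available text, so no claim that the swap would be free of cost can be made.

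Finally, Project 500 is described as preliminary, and the Secondary Objectives already plan to relate early biomarkers to later disease. This limits the consequence but leaves the year-1 interpretation uncorrected.

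**Conclusion.** The point holds as one of interpretation. All wheeze counted under Hypothesis 2 precedes or coincides with the only 25(OH)D measurement. The result can therefore be reported as a cross-sectional association, but not as a risk of developing wheeze or as evidence that 25(OH)D predicts it. Reverse causation in either direction cannot be excluded, and its size is unknown from the documents; the 27% to 92% range rests on assumed shifts of 0.2 to 0.5 SD and a two-sided 5% test.

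The 1-year value could stand in for earlier status if 25(OH)D were stable through infancy, but the Protocol neither states nor supports this. The correction should be made because it changes what the study may conclude at almost no cost. It does not invalidate the hypothesis or require a different exposure.

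**What to change.** - **Statistical section, Hypothesis 2:** state that the 1-year 25(OH)D analysis is cross-sectional. Report it as a prevalence or odds ratio for wheeze to date, and remove the wording about risk of developing wheeze.
- **Rationale, Hypothesis 2:** replace the promise to confirm or negate the associations with one to estimate them.
- **Prospective claim:** reserve it for an analysis of 1-year 25(OH)D against wheeze reported after the draw, using the follow-up already planned to age 5.
- **Optional:** if sample volume and budget allow, measure 25(OH)D in the cord or maternal samples that are to be retrieved. Use it as an added secondary exposure that precedes first-year wheeze, not as a replacement for the hypothesis about infancy.

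The wording changes cost essentially nothing beyond a weaker stated conclusion at year 1. The optional measure adds up to 500 assays for each sample type chosen, at a price the available text does not show.
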